This is an open-label study where all subjects are to receive the Study drug. The study will enroll to treat a minimum of 20 subjects, 2 years of age and older, presenting with 1-6 common warts with the goal of approximately 20 subjects completing all study activities in Cohort 1 per protocol. Cohort 2 will utilize up to 4 sites to enroll approximately 35 subjects (12 years and older). Although no formal power calculations have been performed, it is expected that a sample size of 20 subjects (Cohort 1) and 35 subjects (Cohort 2) evaluable at the EOS/EOT visit (Day 84 for both Cohorts) will be informative regarding wart clearance rates that can support assumptions in subsequent placebo-controlled trials. A sample size of 20 completed subjects for Cohort 1 and approximately 35 subjects for Cohort 2, will provide information to build an adequate safety profile of VP-102 in common warts. The primary analysis will be conducted at Day 84 for both Cohorts. The final analysis will be conducted for Cohort 2 when the last patient has completed the visit on Day 147.

Subjects who receive all planned treatments of VP-102 (e.g., up to four treatments within the 63 day treatment window, or cleared of all treatable warts prior to Day 63 in Cohort 1; and in Cohort 2 complete up to four treatments within the Day 75 treatment window or clear prior to Day 75) and have no major protocol violations are assessed for clearance at the EOS visit and included in the Per Protocol population.

Subject demographics, efficacy tables and subject dropout rates will be tabulated at the end of the study. Data will be summarized using descriptive statistics (sample size, mean, median, standard deviation, minimum, maximum) for continuous variables and frequencies and percentages for discrete variables. Corresponding by-subject data listings will be tabulated.

Adverse events, including local skin reactions, will be coded with the MedDRA® dictionary. The number and percentage of subjects having treatment-emergent AEs will be tabulated by system organ class and MedDRA preferred term with a breakdown by treatment group.

Table 1 Study Schedule of Assessments and Procedures – Cohort 1

	Screening ^a Up to 14 days before Day 1	Treatment 1: Day 1 ^b	24 hr Phone Call ^m +/-4 hrs	Rx 1/Day 7 Phone Call ^m +/- 1 Day	Treatment 2 ^b	24 hr Phone Call ^m +/- 4 hrs	Rx 2/Day 7 Phone Call ^m +/- 1 Day	Treatment 3 ^b	24 hr Phone Call ^m	Rx 3/Day 7 Phone Call ^m +/- 1 Day	Treatment 4 ^b	24 hr Phone Call ^m +/- 4 hrs	Rx 4/Day 7 Phone Call ^m +/- 1 Day	End of Study: Day 84 ^c (+/- 7 days)	Unscheduled Visit ^h
Informed Consent and Authorization	X														
Inclusion/ Exclusion Criteria		X													
Demographics ^d	X														
Height/Weight ^e	X													X	
Prior Relevant Medical History	X	X													
Wart History	X	X													
Prior and Concomitant Medications	X	X	X	X	X	X	X	X	X	X	X	X	X	X	X
Vital Signs (T/P) ^c		X			X			X			X			X	X
Physical Exam ^f	X													X	
Wart Count ^g		X			X			X			X			X	X
Wart Location & Measurement ^g		X			X			X			X			X	
Dermatologic Exam; (includes Fitzpatrick at Screen only) ^g		X			X			X			X			X	X
Urine Pregnancy Test ⁱ		X			X			X			X			X	
Photos (Site/Subject) ^j		X	X		X	X	X	X	X	X	X	X	X	X	
Study Drug Application		X			X			X			X				
Apply Occlusive Tape ^k		X			X			X			X				
ERT Assessments ^l		X	X	X	X	X	X	X	X	X	X	X	X	X	X
Adverse Events		X	X	X	X	X	X	X	X	X	X	X	X	X	X
Take Home Instructions, LSR guide/subject education ^m		X			X			X			X				
Provider Questionnaire ⁿ														X	

EOS = end of study; LSR = local skin reactions; ERT= evaluation of response to treatment; MOP=Manual of Operations; T/P= temperature, pulse;

- a. Screening can occur up to 14 days prior to Study drug application on Day 1. Screening can occur on the same day as Treatment Visit 1/Study drug application. If treatment is not applied on the same day as Screening, wart count, measurement, location of all warts and dermatologic exam must be repeated prior to Study drug application. An IRB-approved ICF/Assent must be signed before any study specific procedures are performed.
- b. Subjects are to be scheduled in 14-day intervals after each treatment. The next Treatment Visit is to be scheduled 14 days after the last treatment or study visit, but only after any LSR has resolved sufficiently to allow evaluation of the treatment site. Treatment should be administered within 4 days of becoming eligible due to resolution of LSRs. The EOS (Day 84) visit is targeted 6 weeks after Treatment Day 4 is completed but may occur as soon as 3 weeks after the final treatment. The 24-hour phone contact may be conducted at +/- 4 hours. The 7-day phone contact may be conducted +/- 1 day. Subjects that exhibit complete clearance prior to EOS will not be required to return to the clinic until EOS Day 84. ERT phone calls will be scheduled and conducted at each two-week treatment interval until the in-person EOS visit or the subject reports recurrence or new warts that require assessment and treatment per protocol.
- c. A final in person safety assessment, ERT, wart count, photos and study completion form will be completed at the Day 84 (EOS) visit for all subjects. EOS conducted outside the Day 84 EOS visit window will be considered a protocol deviation. Treatments may be administered up to Day 63. Subjects that clear or complete treatment prior to EOS will be followed per protocol until the scheduled EOS visit but do not need to complete any remaining Treatment Visits and can receive follow up via telephone until the required in-person EOS visit.
- d. Demographics: date of birth, sex, race/ethnicity will be collected.
- e. Vital signs (e.g., temperature & heart rate) will be obtained at each treatment prior to application of Study drug. Height and weight will be collected at Screening/Day 1 and EOS.
- f. Limited physical examination. Symptom or AE-directed physical examination may be performed if warranted. (See Source/eCRF for a more detailed description)
- g. Dermatologic exam including Fitzpatrick Skin Type, wart count, wart counts (head/neck, chest/abdomen, back/buttocks, groin, upper/lower extremities, including fingers, hands and arms) should be performed identifying the location of each wart and documented on the body map and source as outlined in the MOP. Measurements of warts should be recorded on Day 1 prior to treatment to confirm they meet inclusion criteria of ≤ 10 mm in diameter and ≤ 3 mm in height. Wart counts and assessments are to be completed prior to each treatment application and/or each in-person visit. New warts should be recorded in the corresponding Source/eCRF. Instructions for measuring wart counts and documenting the wart count and measurements are provided in the Manual of Operations (MOP).
- h. "Unscheduled" visits may be completed when clinically warranted. (e.g. if a subject reports signs or symptoms classified as a treatment emergent AE and requires further evaluation) "Unscheduled" visits should also be used for visits where treatment is unable to be applied to all warts due to ongoing LSRs.
- i. To be performed prior to Study drug application and at EOS in any females of childbearing potential (females that are capable of menstruating).
- j. Subjects that agree to participate in the photographic portion of the study will have photos of warts taken prior to each treatment by the study team. If there are no warts remaining, the same areas will be photographed and repeated at the EOS regardless of whether warts are present. Subjects will also be asked to take photos after each treatment at home every 24 hours for 5 days with their phone and either send photos via text or email to the research team or bring them for upload and storage at the next in-person study visit. These images may be used on handouts in future trials, for training purposes or future marketing materials. (Photographs will be de-identified to those outside the research team and stored in a HIPAA compliant manner. Effort will be made to ensure that no photos with identifiable features are obtained).
- k. Occlusive tape and Study drug may be gently removed from individual warts prior to 24 hours of application in the event of significant blistering, significant pain or treatment emergent AEs. The occlusive tape and Study drug should not be removed from the remaining unproblematic warts until the 24-hour time point is reached. Removal of the occlusive tape should be aided by soap and warm water. This will also help to prevent unroofing the blisters. Subjects that remove Study drug prior to 24 hours will be considered a protocol deviation if it does not meet the requirements for early removal as outlined in Section 9.2.2 of the protocol. Early removal is defined by removal at < 16 hours after treatment is applied.

Clinical Protocol – VP-102-105

- l. Phone assessments for ERT will be conducted at 24 hours and at 7 days after each Treatment Visits 1-4 where Study drug is applied. Assessments will be recorded by the research team member on the Evaluation of Response to Treatment (ERT) form. All ERT safety assessments must be conducted by a qualified member of the research team. There will be an additional in-person assessment conducted at Day 84 (EOS) to confirm the presence or absence of warts and record any new or status update of any ongoing treatment related AE's that may have occurred. For subjects that exhibit complete clearance prior to the end of treatment, ERT phone calls will be scheduled and conducted at each two-week treatment interval until the in-person EOS visit or the subject reports recurrence or new warts that require assessment and treatment per protocol.
- m. Subjects will be given take-home instructions describing how to remove the occlusive tape, the possible local skin reactions and what to expect over the next 24 hours to several months. A 24-hour emergency number will also be provided. The next visit date/calls and time will be indicated on the form. A Local Skin Reaction Guide for subjects will be reviewed at the clinic with the subject /guardian by the research team with copies provided for home use in the required 24-hour post treatment follow-up phone calls. Both take home instructions and LSR Guide will be provided and reviewed after each treatment to ensure understanding and confirm the education materials are available.
- n. Provider questionnaire to be completed at EOS by a clinician that applied treatment to the subject during the course of the study.

Table 2 Study Schedule of Assessments and Procedures - Cohort 2

	Screening ^a Up to 14 days before Day 1	Treatment 1: Day 1 ^b	24 hr Phone Call ^m +/-6 hrs	Rx 1/Day 7 Phone Call ^m	Treatment 2 21 days +/- 4 days ^b	24 hr Phone Call ^m +/- 6 hrs	Rx 2/Day 7 Phone Call ^m	Treatment 3/ 21 days +/- 4 days ^b	24 hr Phone Call ^m +/- 6 hrs ^m	Rx 3/Day 7 Phone Call ^m	Treatment 4/ 21 days +/- 4 days ^b	24 hr Phone Call ^m +/- 6 hrs	Rx 4/Day 7 Phone Call ^m	End of Treatment Visit (Day 84) ^c -0/+8 Days	Follow-up visits at 21-day intervals ^p (Day 105, Day 126 and Day 147)	Unscheduled Visit ⁱ
Informed Consent and Authorization	X															
Inclusion/ Exclusion Criteria		X														
Demographics ^d	X															
Height/Weight ^e	X													X		
Prior Relevant Medical History	X	X														
Wart History	X	X														
Prior and Concomitant Medications	X	X	X	X	X	X	X	X	X	X	X	X	X	X	X	X
Vital Signs (T/P) ^e		X			X			X			X			X		X
Physical Exam ^f	X													X		
Wart Location & Measurement ^g		X			X			X			X			X	X	
Dermatologic Exam; (includes Fitzpatrick at Screen only) ^g		X			X			X			X			X	X	X
Paring ^h		X			X			X			X			X		
Urine Pregnancy Test ⁱ		X			X			X			X			X		
Photos (Site/Subject) ^k		X	X		X	X		X	X	X	X	X	X	X	X	
Study Drug Application ^l		X			X			X			X					
Apply Occlusive Tape ^l		X			X			X			X					
ERT Assessments ^m		X	X	X	X	X	X	X	X	X	X	X	X	X	X	X
Adverse Events		X	X	X	X	X	X	X	X	X	X	X	X	X	X	X

Take Home Instructions, LSR guide/subject education ⁿ		X			X			X			X				
Provider Questionnaire ^o													X		

EOS = end of study; EOT=end of treatment; LSR = local skin reactions; ERT= evaluation of response to treatment; MOP=Manual of Operations; T/P= temperature, pulse;

- a. Screening can occur up to 14 days prior to Study drug application on Day 1. Screening can occur on the same day as Treatment Visit 1/Study drug application. If treatment is not applied on the same day as Screening, measurement (height & diameter), location of all warts and dermatologic exam must be repeated prior to Study drug application. An IRB-approved ICF/Assent must be signed before any study specific procedures are performed.
- b. Subjects are to be scheduled in 21-day intervals (+/- 4 days) after each treatment for subjects in Cohort 2. The next Treatment Visit is to be scheduled 21 (+/- 4 days) after the last treatment, but only after any LSR has resolved sufficiently to allow evaluation of the treatment site. The research team should be in contact with the patient until LSRs are resolved and a treatment visit can be scheduled within 21 days (+/- 4) when possible. The 24-hour phone contact may be conducted at +/- 6 hours. The 7-day phone contact may be conducted +/- 24 hrs.
- c. A final in person safety assessment, ERT, photos and study completion form will be completed at the Day 147 (EOS) Visit for all subjects. EOS conducted outside the Day 147 EOS visit window will be considered a protocol deviation. Treatments may be administered up to Day 75 in Cohort 2. Subjects in Cohort 2 are to attend all visits whether they have achieved complete clearance prior to and at the Day 84 (- 0/+ 8 days) EOT assessment.
- d. Demographics: date of birth, sex, race/ethnicity will be collected.
- e. Vital signs (e.g., temperature & heart rate) will be obtained at each treatment prior to application of Study drug. Height and weight will be collected at Screening/Day 1, EOT Day 84 (- 0/+ 8 days) and subsequent follow up visits Day 105, 126 and 147 (EOS).
- f. Limited physical examination. Symptom or AE-directed physical examination may be performed if warranted. (See Source/eCRF for a more detailed description)
- g. Dermatologic exam including Fitzpatrick Skin Type, location of each wart is identified and documented on the body map and source as outlined in the MOP. Measurements of warts should be recorded on Day 1 prior to treatment to confirm they meet inclusion criteria of ≤ 10 mm in diameter and ≤3 mm in height. Wart location, measurements and assessments are to be completed prior to each treatment application and/or each in-person visit. New warts should be recorded in the corresponding Source/eCRF. Instructions for measuring and documenting the and measurements are provided in the Manual of Operations.
- h. Paring at first visit by Dermatologist or qualified designee. Paring at additional treatment visits if significant hyperkeratosis or at Investigator’s discretion.
- i. “Unscheduled” visits may be completed when clinically warranted. (e.g. if a subject reports signs or symptoms classified as a treatment emergent AE and requires further evaluation) “Unscheduled” visits should also be used for visits where treatment is unable to be applied to all warts due to ongoing LSRs.
- j. To be performed prior to Study drug application and at Day 147; (EOS) in any females of childbearing potential (females that are capable of menstruating).
- k. Subjects that agree to participate in the photographic portion of the study will have photos of warts taken prior to each treatment by the study team. If there are no warts remaining, the same areas will be photographed and repeated at the EOT and EOS regardless of whether warts are present. Subjects will also be asked to take photos at 24 hours after each treatment at home with their phone and either send photos via text or email to the research team or bring them for upload and storage at the next in-person study visit. These images may be used on handouts in future trials, for training purposes or future marketing materials. (Photographs will be de-identified to those outside the research team and stored in a HIPAA compliant manner. Effort will be made to ensure that no photos with identifiable features are obtained).

Clinical Protocol – VP-102-105

- l. Occlusive tape and Study drug may be gently removed from individual warts prior to 24 hours of application in the event of significant blistering, significant pain or treatment emergent AEs. The occlusive tape and Study drug should not be removed from the remaining unproblematic warts until the 24-hour time point is reached. Removal of the occlusive tape should be aided by soap and warm water. This will also help to prevent unroofing the blisters. Subjects that remove Study drug prior to 24 hours will be considered a protocol deviation if it does not meet the requirements for early removal as outlined in Section 9.2.2 of the protocol. Early removal is defined by removal at < 16 hours after treatment is applied.
- m. Phone assessments for ERT will be conducted at 24 hours and at 7 days after each Treatment Visits 1-4 where Study Drug is applied. Assessments will be recorded by the research team member on the ERT form. All ERT safety assessments must be conducted by a qualified member of the research team. Subjects in Cohort 2 must attend all visits regardless of whether complete clearance of all warts has been achieved at a previous visit.
- n. Subjects will be given take-home instructions describing how to remove the occlusive tape, the possible local skin reactions and what to expect over the next 24 hours to several months. A 24-hour emergency number will also be provided. The next visit date/calls and time will be indicated on the form. An LSR Guide for subjects will be reviewed at the clinic with the subject /guardian by the research team with copies provided for home use in the required 24-hour post treatment follow-up phone calls. Both take home instructions and LSR Guide will be provided and reviewed after each treatment to ensure understanding and confirm the education materials are available.
- o. Provider questionnaire to be completed at EOT by a clinician that applied treatment to the subject during the course of the study.
- p. Subjects in Cohort 2 will return for follow-up visits on Day 105,126 and 147 (EOS) (+/- 4 days at each visit) for an assessment of warts to determine the durability of previous responses and/or local skin responses.

TABLE OF CONTENTS

1	SYNOPSIS.....	4
	TABLE OF CONTENTS.....	23
	LIST OF IN-TEXT TABLES.....	25
	LIST OF IN-TEXT FIGURES.....	25
	LIST OF ABBREVIATIONS.....	26
2	INTRODUCTION.....	28
2.1	Verruca Vulgaris (common warts).....	28
2.2	Cantharidin.....	29
2.2.1	Nonclinical Studies with Cantharidin	31
2.2.2	Clinical Studies with Cantharidin	32
2.3	Study Rationale.....	34
2.4	Dose and Schedule Rationale.....	34
3	OBJECTIVES.....	35
3.1	Cohort 1: Primary Objectives.....	35
3.2	Cohort 1: Secondary Objectives.....	36
3.3	Cohort 1: Exploratory Objectives.....	36
3.4	Cohort 2: Primary Objectives.....	36
3.5	Cohort 2: Secondary Objectives.....	36
3.6	Cohort 2: Explorative Objective.....	36
4	STUDY DESIGN.....	38
4.1	Basic Design Characteristics.....	38
4.2	Study Population.....	42
4.2.1	Inclusion Criteria	42
4.2.2	Exclusion Criteria	43
4.3	End Points.....	44
4.3.1	Safety	46
4.3.2	Efficacy	48
4.4	Enrollment & Dropouts.....	48
5	DRUGS AND DOSAGES.....	50
5.1	Identification and Description of Investigational Product.....	50

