- Photos taken by subject (per protocol Cohort 1 & 2) Treatment Visit 4:
 - Wart count (Cohort 1),
 - Measurement and location of all warts,
 - Photos (if applicable),
 - Dermatologic exam, ERT,
 - Paring of warts (Cohort 2), if applicable,
 - Study drug application and occlusion with tape (if subject has warts remaining),
 - Removal of occlusive tape and Study drug 24 hours after application,
 - ERT phone call at 24h and day 7,
 - Any new warts should be counted (Cohort 1), measured, documented and treated per protocol,
 - ERT and wart count (Cohort 1) conducted over the phone if cleared at Treatment Visit 3,
 - Photos taken by subject (per protocol Cohort 1 & 2).
- **“Unscheduled” Visit:** May take place at any time, as needed, to evaluate the subjects for safety reasons or for those subjects unable to be treated due to an ongoing LSR. For those subjects evaluated at their scheduled Treatment Visit as exhibiting untreatable warts, no treatment will be administered, and an “Unscheduled” treatment form will be completed. The following information should be obtained:
 - Reason treatment was not administered,
 - Dermatologic exam,
 - ERT, including LSR, wart count (Cohort 1) and location of all warts,
 - Photos (if applicable).
- **Cohort 1: End of Study Visit (EOS Day 84); Cohort 2: End of Treatment Visit (EOT; Day 84)**In person: Vital signs, weight, wart count (Cohort 1),
 - Measurement and location of all warts,
 - Photos (if applicable),
 - Dermatologic exam and ERT,
 - Any new warts should be counted (Cohort 1), measured and documented per protocol,
 - Provider EOS/EOT Treatment Questionnaire.
- **Follow-up Visits Cohort 2: (Day 105, Day 126 and Day 147)**
 - In person: Vital signs,
 - Measurement and location of all warts,
 - Photos (if applicable),

- Dermatological exam and ERT,
- Any new warts should be measured and documented per protocol.

Study Duration:

Cohort 1: Study duration from Treatment Visit 1 through the EOS is approximately 84 days (12 weeks, may extend up to 98 days). No treatment should be administered after Day 63 without Sponsor's approval.

Cohort 2: Study duration from Treatment Visit 1 through the final follow-up is approximately 147 days (21 weeks). No treatment should be administered after Day 75 without Sponsor's approval. Post-treatment follow-up visits are included for subjects in Cohort 2 to evaluate the durability of treatment response over time.

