7.3. Demographic and Baseline Characteristics

Demographics variables will include: age, sex, ethnicity and race. For summary purposes, age will be derived by comparing date of birth to date of informed consent.

Baseline characteristics will include: relevant medical history, wart history (including prior treatment), Fitzpatrick Skin Type, height, weight and body mass index (BMI). BMI will be calculated by weight (kg) / height (m²). Wart history variables that will be summarized include time since clinical diagnosis (as compared to informed consent), age at clinical diagnosis and any previous treatments for warts. Time since clinical diagnosis will be derived by comparing the date of informed consent to date of clinical diagnosis. Time since clinical diagnosis will be expressed in months using the following conversion: (12 * days) / 365.25. In the event the date of clinical diagnosis is not complete (“partial date”), the date will be imputed with the earliest date possible. As an example, if only the month and year are known for date of clinical diagnosis, the first day of the month will be used for imputation purposes.

Age at clinical diagnosis will be derived by comparing date of clinical diagnosis to date of birth. Incidence of the following prior wart treatment categories will be tabulated: Cantharidin, Anti-Virals, Retinoids, Salicylic Acid, Curettage, Freezing, Other. Relevant medical history will not be summarized in a table but will be displayed in a listing.

Continuous variables will be summarized using descriptive statistics. Categorical variables will be summarized using counts and percentages. Demographics, baseline characteristics, wart history and prior wart treatment will be summarized for all 3 analysis populations (ITT, Safety, Per Protocol).

8. Efficacy Analysis

The ITT and Per Protocol population will be used for efficacy analysis. Analyses based on the ITT population will be considered the primary analyses. Results will be summarized using descriptive statistics and counts/percentages. For select endpoints, 95% confidence intervals may be generated as well.

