8.1. Efficacy Variables

Primary endpoint:

- Proportion of subjects exhibiting complete clearance of all treatable warts (baseline and new) at the End of Treatment (EOT) Visit (Day 84).

Secondary endpoints:

- Change from baseline in the number of treatable warts (baseline and new) at the EOT visit (Day 84).
- Change from baseline in the percent of treatable warts (baseline and new) at the EOT visit (Day 84).
- Proportion of subjects exhibiting complete clearance of all treatable warts (baseline and new) at Treatment Visit 2, Treatment Visit 3, Treatment Visit 4.

Exploratory endpoints:

- Percent reduction of all treatable warts (baseline and new) from baseline at Treatment Visit 2, Treatment Visit 3, Treatment Visit 4.
- Change from baseline in the number of treatable warts (baseline and new) at Treatment Visit 2, Treatment Visit 3, Treatment Visit 4.
- Proportion of subjects exhibiting $\geq 50\%$ clearance of all treatable warts (baseline and new) at the EOT visit as compared to baseline.
- Proportion of subjects who respond to treatment defined by a $\geq 50\%$ reduction in total wart area at EOT visit compared to baseline.
- Proportion of subjects exhibiting reduction of at least 1 treatable wart from baseline at Treatment Visit 2, Treatment Visit 3, Treatment Visit 4 and at the EOT Visit.
- Proportion of subjects exhibiting complete clearance of all treatable warts (baseline and new) at follow-up visits on Day 105, Day 126 and Day 147.
- Percent reduction of all treatable warts (baseline and new) from baseline at follow-up visits on Day 105, Day 126 and Day 147.
- Change from baseline in the number of all treatable warts (baseline and new) from baseline at follow-up visits on Day 105, Day 126 and Day 147.

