9.1. Complete Clearance of Treatable Warts

Counts and percent of subjects who have complete clearance of all treatable warts (baseline and new) will be displayed by visit. Complete clearance will be defined as no warts (treatable wart count=0) reported for a subject per the Wart Location and Measurement form. Number of common warts (treatable and untreatable) at unscheduled visits will be displayed in listings.

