9.2. Change and Percent Change in Number of Warts

Number of warts present will be determined by the number of wart forms filled out with a wart diameter >0mm at each treatment visit as well as the EOT visit and 3 follow-up visits. For each post baseline treatment visit, the change in number of warts from baseline will be calculated. Summary statistics of number of warts will be displayed for each post baseline visit. Summary statistics of change in number of warts from baseline will also be displayed.

Percent change of warts will be calculated for each post baseline visit. Percent change will be calculated using the following formula (in formula below, warts refers to treatable warts):

$$\text{Percent (\%) Change} = \left(\frac{\text{Warts at Post Baseline Visit} - \text{Warts at Baseline Visit}}{\text{Warts at Baseline Visit}} \right) * 100$$

Analysis of percent change in number of warts will be carried out in the same manner as change in number of warts.

As described in Section 8.4.3, should any combined warts be reported, sensitivity analysis will be carried for change and percent change endpoints in which the number of warts which merge to create a combined wart will be imputed for all subsequent visits until the combined wart has cleared.

Section 8.4.2 specifies that the LOCF method will be used to impute result for visits with missing wart counts. This includes imputation of all treatment and follow up visits as well as the EOT visit. To investigate the potential impact the LOCF method could have on table summaries for change/percent change wart counts, an additional set of sensitivity analysis will be carried which only considers wart counts reported with no imputation. The analysis will be identical to the analysis described above, with the only difference being whether imputation is carried out or not.

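### Cohort 2 is followed to Day 147 to assess durability, but every planned follow-up summary is a by-visit figure not conditioned on Day 84 clearance, which can leave durability largely unidentified

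*Protocol*

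**What the plan says.** **Purpose of the visits.** The Study Duration paragraph of the protocol synopsis says that the Cohort 2 visits after treatment are there to "evaluate the durability of treatment response over time". Footnote p to Table 2 says that subjects return on Days 105, 126 and 147 "for an assessment of warts to determine the durability of previous responses and/or local skin responses".

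**Planned analysis.** SAP 8.1 lists three exploratory follow-up endpoints, matching Protocol 4.3: complete clearance, percent reduction in warts and change in wart number. The first reads: "Proportion of subjects exhibiting complete clearance of all treatable warts (baseline and new) at follow-up visits on Day 105, Day 126 and Day 147". SAP 9.1 gives the method: "Counts and percent of subjects who have complete clearance of all treatable warts (baseline and new) will be displayed by visit". SAP 9.2 summarises counts, change and percent change by visit. SAP 9.3 adds two by-visit categories: at least 50% reduction, and reduction of at least one wart. On the population, SAP Section 8 says: "Analyses based on the ITT population will be considered the primary analyses". The ITT population is everyone enrolled. The possible subgroups in SAP 8.7 do not include Day 84 clearers.

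**Missing data.** SAP 8.4.1 scores a missing clearance assessment as not cleared at that visit. SAP 8.4.2 carries the last wart count forward, and SAP 9.2 says of that rule: "This includes imputation of all treatment and follow up visits as well as the EOT visit". SAP 9.2 also plans a sensitivity analysis without imputation for change and percent change in counts.

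**Return of a wart.** SAP Section 8 records a returned wart by its diameter and uses this to set that wart's status at the visit.

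**The concern.** A previous response belongs to a subject who has already responded. Its durability is therefore a within-subject question: of those clear at Day 84, how many stayed clear? Neither document defines sustained clearance or recurrence among Day 84 clearers, and neither plans a time to recurrence or a table of Day 84 status against later status.

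A by-visit proportion moves by the difference between subjects lost from clearance and subjects newly clear. A flat line can mean that nobody changed, or that many changed in both directions. A rising line can be late clearance alone.

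Late clearance is possible on the documents' own terms. Treatment may be given up to Day 75 (Table 2, footnote c), which is 84 − 75 = 9 days before the Day 84 assessment. SAP Section 3 notes that skin reactions can make clearance hard to judge. Protocol 2.1 notes that warts resolve spontaneously, although this can take years.

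At stake is whether the reported results answer the question for which subjects make three more visits. The synopsis also says that the study should inform assumptions for later placebo-controlled trials.

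**Working it through.** The plan has no figure of its own to reproduce: about 35 subjects are enrolled in Cohort 2 and no formal sample-size calculation is made. The documents give no Cohort 2 rate of clearance, recurrence or late clearance, so the clearance counts below are assumptions, shown over a range.

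**Step 1: what two by-visit proportions reveal, with complete data.** Let *n* = 35, *a* = number clear at Day 84 and *b* = number clear at Day 147. The number of Day 84 clearers no longer clear at Day 147, *L*, satisfies

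max(0, *a* − *b*) ≤ *L* ≤ min(*a*, *n* − *b*),

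and sustained clearance is (*a* − *L*)/*a*.

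| Clear at Day 84 | Clear at Day 147 | Possible *L* | Possible sustained clearance |
|---|---|---|---|
| 7 | 7 | 0 to 7 | 0% to 100% |
| 13 | 13 | 0 to 13 | 0% to 100% |
| 18 | 18 | 0 to 17 | 5.6% (1/18) to 100% |
| 20 | 20 | 0 to 15 | 25.0% (5/20) to 100% |
| 25 | 25 | 0 to 10 | 60.0% (15/25) to 100% |
| 18 | 15 | 3 to 18 | 0% to 83.3% (15/18) |
| 18 | 20 | 0 to 15 | 16.7% (3/18) to 100% |

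**Step 2: what the conditional proportion adds.** Take 18/35 clear at Day 84 and match each loss with one late clearance. The planned Day 147 figure is 18/35 = 51.4% every time. The proportion among the 18, with exact (Clopper-Pearson) 95% intervals, separates the cases:

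| Lost | Late clearers | Still clear among the 18 |
|---|---|---|
| 0 | 0 | 18/18 = 100% (81.5 to 100) |
| 3 | 3 | 15/18 = 83.3% (58.6 to 96.4) |
| 6 | 6 | 12/18 = 66.7% (41.0 to 86.7) |
| 9 | 9 | 9/18 = 50.0% (26.0 to 74.0) |

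**Step 3: missing data.** Suppose 18 are clear at Day 84, nobody clears late, and either

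- four clearers miss Day 147 and none loses clearance, or
- none is missing and four lose clearance.

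Under SAP 8.4.1 both give (18 − 4)/35 = 14/35 = 40.0%, so dropout looks like recurrence. Among the 18, scoring missing as not maintained also gives 14/18 = 77.8% (52.4 to 93.6) in both cases. Observed cases separate them: 14/14 = 100% (76.8 to 100) against 14/18.

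In the count tables the direction reverses. A subject with a count of zero at Day 84 who then leaves keeps zero at Days 105, 126 and 147. The no-imputation analysis in SAP 9.2 removes this for change and percent change in counts, but it too is a by-visit summary.

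**The case against.** The strongest reply is that the formal objective is met. Protocol 3.6 and SAP 2.2.3 ask for the proportion of subjects clear on Days 105, 126 and 147, and the planned endpoint is exactly that. Durability appears in a study-duration sentence and a table footnote, and the footnote also names local skin responses. The endpoints are exploratory, in a descriptive study of about 35 subjects. Subject listings would let a reader trace recurrence by hand, and SAP Section 5 allows labelled post hoc analyses.

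Most of this is correct, and it limits how serious the point is. It does not remove it. The protocol gives durability as the reason for the visits, and no planned summary is conditional on having responded. If the analysis is left to the listings, the denominator, the missing-data rule and the meaning of maintained clearance would be chosen after the results are seen.

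Two stronger readings are tempting, and the documents support neither:

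- *Late clearance does offset recurrence here, so the planned figures cannot show durability at all.* Offsetting is possible but not established. With complete data, a fall in the proportion sets a minimum on loss of clearance (18 to 15 means at least 3), and a high Day 84 rate narrows the range.
- *Carrying values forward leaves departed responders counted as clear throughout.* This applies to the count-based tables only. The clearance table scores them as not clear, and the no-imputation analysis covers change and percent change in counts.

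**Conclusion.** The point holds in a limited form. The planned follow-up summaries can leave durability largely unidentified: 5.6% to 100% sustained clearance with 18/35 clear at both visits, and 60% to 100% with 25/35. These ranges assume 35 subjects, complete data and clearance counts that the documents do not supply. They are limits of what is possible, not forecasts. Missing data add distortion in opposite directions in the clearance and count tables. Because new warts count against clearance, loss of clearance is also not the same as recurrence of a treated wart. The Day 84 primary endpoint is unaffected. The change is worth making before database lock, but the study does not depend on it.

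**What to change.** Add to SAP 9.1, as an exploratory analysis using the visit windows already defined in SAP Section 8:

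1. Among subjects completely clear at EOT, the number and percentage still clear at Day 105, at Day 126, at Day 147 and at all three, with exact 95% confidence intervals. Score missing as not maintained, and show observed cases as a sensitivity analysis.
2. A table of Day 84 status against status at each follow-up visit, with missing as its own category. This shows late clearers separately and keeps dropout apart from loss of clearance.
3. Loss of clearance split into return of a previously cleared wart and appearance of a new wart.

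No new data, visits or procedures are needed: the SAP already records return of a cleared wart, and Protocol 6.2.6 has new warts documented at follow-up. The cost is one extra table's worth of programming, and wide intervals from a small denominator. With an assumed 18 clearers, 15/18 carries an interval of 58.6% to 96.4%, so the result should be presented as descriptive.
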